### **10.3.4. Complaint Handling**

Lilly collects product complaints of investigational products and drug delivery systems used in clinical studies in order to ensure the safety of study participants, monitor quality, and to facilitate process and product improvements.

The investigator or his/her designee is responsible for handling the following aspects of the product-complaint process in accordance with the instructions provided for this study:

- recording a complete description of the product complaint and any associated AEs using study-specific product-complaint forms, which are provided for this purpose
- faxing the completed study-specific product-complaint form within 24 hours to Lilly or its designee

If the investigator is asked to return the product for investigation, he/she will return a copy of the study-specific product-complaint form along with the product.

## **10.4. Sample Collection and Testing**

[Attachment 1](#) lists the schedule for sample collections in this study.

[Attachment 2](#) lists the specific laboratory tests that will be performed for this study.

[Attachment 3](#) provides a summary of the estimated maximum number and volume of samples, for all sampling, during the study.

### **10.4.1. Samples for Study Qualification and Health Monitoring**

Blood and urine samples will be collected at the times specified in the Study Schedule ([Attachment 1](#)). Standard laboratory tests, including chemistry and hematology will be performed. The clinical laboratory tests including a pregnancy test will be performed at a central laboratory. A urine pregnancy test may be repeated locally for any visits if considered necessary by the investigators and/or in compliance with local regulations. [Attachment 2](#) lists the specific tests that will be performed for this study.

Investigators must document their review of each laboratory safety report.

Samples collected for specified laboratory tests will be destroyed within 60 days of receipt of the confirmed test results. Tests are run and confirmed promptly whenever scientifically appropriate. When scientific circumstances warrant, however, it is acceptable to retain samples to batch the tests run, or to retain the samples until the end of the study to confirm that the results are valid. Certain samples may be retained for a longer period, if necessary, to comply with applicable laws, regulations, or laboratory certification standards.

### **10.4.2. Samples for Biomarker Research**

#### **10.4.2.1. Nonpharmacogenetic Biomarker Evaluations**

This study will employ sample collection. Samples will be collected for nonpharmacogenetic biomarker investigation where local regulations allow. Fasting serum samples will be collected at the times specified in the Study Schedule ([Attachment 1](#)).

Fasting samples being collected will be used to measure C-peptide to support trial interpretation.

Samples will be coded with the patient number and may be stored for a maximum of 1 year following last patient visit for the trial at a facility selected by the Sponsor to enable further analysis of responses to the investigational products. The duration allows the Sponsor to respond to regulatory requests related to the investigational products.

### **10.4.3. Samples for Immunogenicity Research**

Blood samples for immunogenicity testing will be collected to determine antibody production against LY2963016 or Lantus®. Immunogenicity will be assessed by a validated assay designed to detect anti-glargine antibodies in the presence of the investigational product. Antibodies may be further characterized and/or evaluated for their ability to neutralize the activity of the LY2963016 or Lantus®.

Samples may be stored for a maximum of 1 year following last patient visit for the trial at a facility selected by the sponsor to enable further analysis of immune responses to LY2963016 or Lantus®. The duration allows the sponsor to respond to regulatory requests related to the investigational product.

### **10.5. Appropriateness of Measurements**

All efficacy and safety assessments included in this study are generally regarded as reliable and accurate with respect to diabetes mellitus.

## 11. Data Quality Assurance

To ensure accurate, complete, and reliable data, Lilly or its representatives will do the following:

- provide instructional material to the study sites, as appropriate
- sponsor a start-up training session to instruct the investigators and study coordinators. This session will give instruction on the protocol, the completion of the CRFs, and study procedures
- make periodic visits to the study site
- be available for consultation and stay in contact with the study-site personnel by mail, telephone, and/or fax
- review and evaluate CRF data and use standard computer edits to detect errors in data collection
- conduct a quality review of the database

In addition, Lilly or its representatives will periodically check a sample of the patient data recorded against source documents at the study site. The study may be audited by Lilly or its representatives and/or regulatory agencies at any time. Investigators will be given notice before an audit occurs.

To ensure the safety of participants in the study, and to ensure accurate, complete, and reliable data, the investigator will keep records of laboratory tests, clinical notes, and patient medical records in the patient files as original source documents for the study. If requested, the investigator will provide the Sponsor, applicable regulatory agencies, and applicable ERBs with direct access to original source documents.

### 11.1. Data Capture System

An electronic data capture system will be used in this study. The site maintains a separate source for the data entered by the site into the Sponsor-provided electronic data capture system.

Case report form data will be encoded and stored in a clinical trial database. Data managed by a central vendor, such as laboratory test data or will be stored electronically in the central vendor's database system. Data will subsequently be transferred from the central vendor to the Lilly generic labs system.

Any data for which the paper documentation provided by the patient will serve as the source document will be identified and documented by each site in that site's study file. Paper documentation provided by the patient may include, for example, a paper diary to collect PRO measures (for example, a rating scale), a daily dosing schedule, or an event diary.

Data from study-specific product-complaint forms submitted to Lilly will be encoded and stored in the global product-complaint management system.

## 12. Sample Size and Statistical Methods

### 12.1. Determination of Sample Size

Based on the primary objective, to show noninferiority of LY2963016 to Lantus® at the 0.40% noninferiority margin (NIM), 450 completers in total with a ratio 2:1 (LY2963016 versus Lantus®) are needed at 24 weeks. This calculation assumes no treatment difference in HbA1c between LY2963016 and Lantus®, common SD of 1.3% for change from baseline in HbA1c, 0.05 two-sided significance level, and over 85% power. Assuming a 15% dropout rate at 24 weeks, the required number of randomized patients is 530 in total (353 for LY2963016 and 177 for Lantus®).

### 12.2. Statistical and Analytical Plans

#### 12.2.1. General Considerations

All data will be entered, verified, and archived by a contract research organization (CRO) external to Lilly and/or at Lilly. Data listings, summaries, and analyses will be performed by a CRO and/or by Lilly under the guidance and approval of statisticians at Lilly. Statistical analysis of this study will be the responsibility of Lilly.

Any change to the data-analysis methods described in the protocol will require an amendment ONLY if it changes a principal feature of the protocol. Any other change to the data analysis methods described in the protocol, and the justification for making the change, will be described in the statistical analysis plan and/or in the clinical study report (CSR). Additional exploratory analyses will be conducted as deemed appropriate.

The patient populations used in the study are described below:

1. All Patients Entered - all patients who entered this study and completed Visit 1
2. All Randomized - all patients who were randomized to a treatment arm
3. Full Analysis Set (FAS) - based on the intent to treat (ITT) principle, all patients who were randomized and who have taken at least one dose of study medication will be included in this analysis set. Patients will be analyzed according to the treatments to which they were randomized.
4. Per-protocol (PP) - patients in the FAS/ITT population who also meet the following criteria:
  - a. have no violations of Inclusion/Exclusion Criteria
  - b. have not discontinued from the study prior to 24 weeks
  - c. have not been off study medication for more than 14 consecutive days during the treatment period
  - d. have not received chronic (lasting longer than 14 consecutive days) systemic glucocorticoid therapy (excluding topical, intra-articular, intraocular, and inhaled preparations)

Efficacy and safety analyses will be conducted using the FAS population. Selected analyses will be conducted using the All Randomized population and the PP population.

Unless otherwise noted, all tests of treatment effects will be conducted at a 2-sided alpha level of 0.05, and confidence intervals (CIs) will be calculated as 2-sided 95% CIs. All tests of interactions between treatment groups and other factors will be conducted at a 2-sided alpha level of 0.05. No adjustments for multiplicity will be performed.

The baseline is Visit 2. If baseline data are missing, the last measurement taken prior to this visit will be used for the baseline measurement.

The analysis of the continuous secondary efficacy and safety measurements will use the same mixed model repeated measure (MMRM) model for the primary efficacy analyses with the baseline value of the response as a covariate with the FAS patient population. Continuous laboratory measures will be analyzed using an analysis of covariance (ANCOVA) model. For categorical measures, Fisher's exact test or Pearson's Chi-square test will be used.

All analyses will be implemented using SAS Version 8.2® or higher.

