5.2. Statistical and Analytical Plans

5.2.1. General Considerations

All data will be entered, verified, and archived by a contract research organization (CRO) external to Lilly and/or at Lilly. Data listings, summaries, and analyses will be performed by a CRO and/or by Lilly under the guidance and approval of statisticians at Lilly. Statistical analysis of this study will be the responsibility of Lilly.

Any change to the data-analysis methods described in the protocol will require an amendment ONLY if it changes a principal feature of the protocol. Any other change to the data analysis methods described in the protocol, and the justification for making the change, will be described in the statistical analysis plan and/or in the clinical study report (CSR). Additional exploratory analyses will be conducted as deemed appropriate.

The patient populations used in the study are described below:

1. All Patients Entered - all patients who signed ICF
2. All Randomized - all patients who were randomized to a treatment arm
3. Full Analysis Set (FAS) - based on the intent to treat (ITT) principle, all patients who were randomized and who have taken at least one dose of study medication will be included in this analysis set. Patients will be analyzed according to the treatments to which they were randomized.
4. Per-protocol (PP) - patients in the FAS/ITT population who also meet the criteria in Trial Issue Management Plan (TIMP), and treatment group will be defined on the basis of the treatment the patients actually receive:
 - a. have no violations of Inclusion/Exclusion Criteria specified in TIMP
 - b. have not discontinued from the study prior to 24 weeks
 - c. have not been off study medication for more than 14 consecutive days during the treatment period

- d. have not received chronic (lasting longer than 14 consecutive days) systemic glucocorticoid therapy (excluding topical, intra-articular, intraocular, and inhaled preparations)
- e. Missing HbA1c at baseline and/or at primary endpoint (week 24; only for subjects who should have V18)

Unless otherwise specified, listings will be prepared using all randomized patients. Efficacy and safety analyses will be conducted using the FAS population. Selected analyses will be conducted using the All Randomized population and the PP population.

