5.2.11. Safety Analyses

5.2.11.1. Adverse Events

Analyses of adverse events will include all data collected during the course of the entire study including the follow up visit, regardless of IP use.

Adverse events will be listed by patient, system organ class, Medical Dictionary for Regulatory Activities® (MedDRA) preferred term, severity, and relationship to the study disease, drug, device, or procedure for all patients. Adverse events (including injection site reactions, allergic events, and neoplasms) will be summarized as TEAEs for the FAS. Treatment-emergent adverse events are defined as events that are newly reported after first study treatment following randomization or reported to have worsened in severity from baseline. The proportion of patients experiencing each TEAE will be presented by preferred term, system organ class (SOC), and treatment group. The proportion of patients experiencing each TEAE that is assessed as possibly related to the study disease, drug, device, or procedures will also be summarized. The number of patients and proportion will be presented and compared by treatment using Fisher's

exact test or Pearson's chi-square test for the FAS population. TEAE will be summarized by preferred term within SOC and by preferred term by decreasing frequency.

All SAEs will be listed by patient and summarized by treatment as counts and percentages. If a sufficient number of SAEs are reported, the proportion of patients with SAEs between treatment groups will be compared using Fisher's exact test. Similar analyses will be performed for discontinuations due to AEs.

Summary table of historical conditions and pre-existing condition will be listed by preferred term and ordered by decreasing order of the total group. Historical conditions are conditions that end prior to inform consent and preexisting conditions are conditions that are still ongoing at inform consent or the conditions that started after inform consent and before first does.

A listing of subjects discontinue IP or study due to adverse event including death will be presented.

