5.2.11.2. Hypoglycemic Events

A **hypoglycemic episode** is that at any time a patient feels as he/she is experiencing a sign or symptom that is associated with hypoglycemia or has a BG level of ≤ 70 mg/dL (≤ 3.9 mmol/L), even if it was not associated with signs, symptoms, or treatment.

Severe hypoglycemia: an event requiring assistance of another person to actively administer carbohydrates or glucagon or take other corrective actions. Plasma glucose concentrations may not be available during an event, but neurologic recovery following the return of plasma glucose to normal levels is considered sufficient evidence that the event was induced by low plasma glucose concentration.

Nocturnal hypoglycemia: any total hypoglycemic event that occurs after bedtime and prior to the first meal upon waking (eg, breakfast).

Documented symptomatic hypoglycemia: an event during which typical symptoms of hypoglycemia are accompanied by a measured plasma glucose concentration ≤ 70 mg/dL (≤ 3.9 mmol/L).

Asymptomatic hypoglycemia: an event not accompanied by typical symptoms of hypoglycemia but with a measured plasma glucose concentration ≤ 70 mg/dL (≤ 3.9 mmol/L).

Probable symptomatic hypoglycemia: an event during which symptoms typical of hypoglycemia are not accompanied by a plasma glucose determination but that was presumably caused by a plasma glucose concentration ≤ 70 mg/dL (≤ 3.9 mmol/L).

Besides the hypoglycemic categories listed above, total hypoglycemic event will be defined as follows:

Total hypoglycemic event: any event which is either documented symptomatic hypoglycemia, asymptomatic hypoglycemia, probable symptomatic hypoglycemia or severe hypoglycemia.

For each category of hypoglycemia event, the incidence, the number of hypoglycemic events per patient, the rate of hypoglycemic events per year (that is, the number of hypoglycemic episodes per patient per patient year [365.25 days]) will be calculated. These measures will be summarized at baseline, titration, maintenance, and overall study periods and at endpoint.

The proportion of patients with at least 1 hypoglycemic event (total, severe, nocturnal, and others) or incidence during the study will be summarized (counts and percentages) and analyzed using Fisher's exact test or the Pearson's chi-square test for the FAS population.

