Logistic regression will be used as a sensitivity analysis of the incidence of hypoglycemia. The model will have presence or absence of hypoglycemia as the dependent or response variable and treatment, baseline HbA_{1c}, and entry use of insulin scretagogue (SU, meglitinide, neither) as the independent terms in the model.

The rate of hypoglycemic episodes per year (total, severe, nocturnal, and others) will be analyzed at baseline, titration, maintenance, and overall study periods and at endpoint using the Wilcoxon test. In addition, the hypoglycemia rates will also be analyzed using a negative binomial model for the FAS population with terms for treatment, baseline HbA_{1c}, and entry use of insulin scretagogue (SU, meglitinide, neither).

In addition, the total number of patients with at least 1 hypoglycemic episode divided by the total extent of exposure in patient-years will be calculated for the overall study period and summarized descriptively for each treatment group for total, severe, nocturnal, documented symptomatic, asymptomatic hypoglycemia and probable symptomatic hypoglycemia. Individual patient listing of hypoglycemic events by visit will be presented for the FAS population.

All the above analysis will be repeated with the threshold of **Clinically significant hypoglycemia:** < 54 mg/dL (3.0 mmol/L) for hypoglycemia categories of total hypoglycemia,

nocturnal hypoglycemia, documented symptomatic hypoglycemia and asymptomatic hypoglycemia.

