5.2.11.4. Laboratory Measures – Insulin Antibodies

At each visit (baseline, visits 4, 6, 12, and 24-week (last observation carried forward [LOCF])), total insulin antibody status and its level of total percent binding will be collected. The lower limit of detection of total insulin antibodies is 1.19%. If antibodies are detected then cross reactive antibody status and its level of cross-reactive percent binding will be recorded. The lower limit of detection of cross-reactive antibodies is 1%.

Descriptive and inferential analyses will be performed for the set of FAS patients with a valid antibody testing (detected or ND) at baseline and at least one post baseline visit.

The proportion of patients with detected insulin antibodies will be summarized as counts and percentages at baseline, at each visit, at the 24-week endpoint (LOCF), and overall for the 24-week treatment period. At each of these time points, the proportion of patients with detected antibodies will be compared between treatment groups using Fisher's exact test. These analyses will be performed for patients with antibody levels detectable at baseline and for patients without detectable levels at baseline) in the FAS population.

In addition, the following listing will be provided for patients with detectable insulin antibodies at any time during the study: a listing of level of total insulin antibody percent binding across visits sorted by treatment and maximum postbaseline percent binding in descending order. Similar listings sorted by baseline percent binding as well as by endpoint percent binding will be provided. These listings will be provided for the FAS population.

The level of detectable insulin antibodies (expressed as percent binding) will be summarized by descriptive statistics (mean, median, SD, Q1, inter-quartile range (IQR), Q3, standard error, minimum, and maximum) at baseline, each visit, and endpoint (LOCF). At each of these time points, the median level of percent binding will be compared between treatment groups using the

Wilcoxon rank sum test. Graphical displays of median percent binding and IQR at each visit and endpoint (LOCF) by treatment will be presented. These analyses will be performed for the FAS population, for patients with antibody levels detectable at baseline and without detectable levels at baseline.

All of the analyses above will be performed for the level of cross-reactive antibodies as well.

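### Safety, hypoglycemia and antibody comparisons group patients by randomized insulin; the SAP uses the insulin actually received only for the per-protocol set

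*Protocol*

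**What the plan says.** Protocol 12.2.1 and SAP 5.2.1 give the same FAS definition: randomized patients who took at least one dose, with the rule "Patients will be analyzed according to the treatments to which they were randomized". Both then state "Efficacy and safety analyses will be conducted using the FAS population". Neither lists a separate safety set.

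The SAP's safety sections repeat this choice:

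- **Adverse events (SAP 5.2.11.1):** events "will be summarized as TEAEs for the FAS". Allergic events (SAP 5.2.11.1.1) are also compared in the FAS.
- **Hypoglycemia incidence (SAP 5.2.11.2):** "analyzed using Fisher's exact test or the Pearson's chi-square test for the FAS population".
- **Hypoglycemia rates (SAP 5.2.11.2):** "the hypoglycemia rates will also be analyzed using a negative binomial model for the FAS population".
- **Antibodies (SAP 5.2.11.4):** "Descriptive and inferential analyses will be performed for the set of FAS patients with a valid antibody testing" at baseline and at least once afterwards.

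The one rule based on product taken is in the SAP's per-protocol (PP) definition: "treatment group will be defined on the basis of the treatment the patients actually receive". The protocol's PP definition has no such clause. The SAP also ties PP membership to criteria in a Trial Issue Management Plan (TIMP), which is not among the documents reviewed.

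**The concern.** Grouping as randomized is the right rule for FAS efficacy. Safety and immunogenicity ask a different question: what happened to patients exposed to each product. Comparing anti-glargine antibodies, hypoglycemia and injection-site reactions between the two insulins is a secondary objective (Protocol 6.2), and samples are drawn to detect antibody production against either product (Protocol 10.4.3). A patient randomized to one insulin who takes the other would have any reaction or antibody response filed under the product not taken.

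In a trial meant to show that two products behave alike, this misfiling works on average toward similarity. The SAP has a rule for patients whose received product differs from the assigned one, but applies it only to a supportive efficacy analysis and not to safety.

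**Working it through.** **1. The plan's own design figures reproduce and are not affected.** Inputs from Protocol 12.1 and SAP 5.1: margin 0.40%, SD 1.3%, 450 completers at 2:1 (300 and 150), two-sided 0.05, 15% dropout, 530 randomized (353 and 177).

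- SE = 1.3 × √(1/300 + 1/150) = 1.3 × 0.10 = 0.13.
- Power = Φ(0.40/0.13 − 1.96) = Φ(1.117) = 86.8% (86.7% with the noncentral t on 448 df). This agrees with the stated power of over 85%.
- 450/0.85 = 529.4, rounded up to 530.

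The primary analysis stays on the FAS as randomized, so nothing below changes these figures.

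**2. Dilution in an as-randomized safety comparison.** Let p₁ and p₂ be the event risks on LY2963016 and Lantus, and suppose risk follows the product taken. Let m patients in each arm take the other product throughout, so f₁ = m/353 and f₂ = m/177.

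- Observed LY2963016 arm: p₁(1 − f₁) + p₂f₁
- Observed Lantus arm: p₂(1 − f₂) + p₁f₂
- Observed difference: (p₁ − p₂) × (1 − f₁ − f₂)

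The documents give no wrong-product rate, so m is an assumption, shown over a range:

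| m per arm | 1 − m/353 − m/177 | A true 10.0-point difference appears as |
|---|---|---|
| 0 | 100% | 10.0 |
| 1 | 99.2% | 9.9 |
| 2 | 98.3% | 9.8 |
| 5 | 95.8% | 9.6 |
| 10 | 91.5% | 9.2 |

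If 10 patients switched in one direction only, 97.2% (LY2963016 arm only, 1 − 10/353) or 94.4% (Lantus arm only, 1 − 10/177) would remain.

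**3. One misattributed patient.** An event filed in the wrong arm shifts that arm's incidence by 1/353 = 0.28 points or 1/177 = 0.56 points. This matters only for rare events.

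**4. Partial exposure.** Pens are dispensed at Visits 2, 6, 10, 12, 14 and 16, that is, Weeks 0, 4, 8, 12, 16 and 20 (Protocol Attachment 1). One wrong dispensing covers about 4 of 24 weeks, so by exposure it counts as roughly one-sixth of a switched patient. The table therefore overstates the effect of isolated errors.

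**The case against.** The strongest reply is that there may be no such patients. Assignment is by IWRS (Protocol 9.3), and in this open-label trial patients, sites and monitors all know the product (Protocol 9.7), so masked-kit mix-ups cannot arise. The actual-treatment clause may be routine wording. Important deviations are listed and summarized by arm (SAP 5.2.6), and adverse and allergic events are listed by patient, so a wrong-product case flagged as a deviation could be traced. All of this stands and limits the size. It does not supply a grouping rule: the tables and tests would still use the randomized product.

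Five stronger readings are tempting, and the documents do not support them:

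- **That the PP set keeps wrong-product patients and relabels them when it should exclude them.** A reader might infer this because PP criteria (a) to (e) do not name wrong-product use. The TIMP adds criteria that cannot be seen here. Criterion (c), on time off study medication, might also be read as meaning assigned medication. Exclusion over regrouping is partly a matter of preference.
- **That PP relabelling dilutes the difference toward noninferiority.** A patient who took the other insulin throughout and is grouped by product received causes no dilution; the cost is a departure from the randomized comparison. Only mixed exposure could dilute, and the analysis is supportive.
- **That dilution could be about 4%.** That needs 2% of each arm (about 7.1 + 3.5 = 10.6 patients) on the wrong product for all 24 weeks, or about 64 wrong dispensings out of 530 × 6 = 3,180. At an assumed error rate of 0.1% there would be about 3. Neither rate has a source in the documents.
- **That one misfiled patient moves a third of severe hypoglycemia.** If the rates of Study ABEC (0.5% and 0.8%, Protocol 5) applied, about 353 × 0.005 + 177 × 0.008 = 3.2 such patients are expected. The misfiled patient would have to be one of them. Even at 3 wrong dispensings in different patients, the expected overlap is about 3.18 × 3.18/530 = 0.02.
- **That every safety analysis uses the FAS.** Protocol 12.2.9.3 summarizes SAEs for all randomized patients. That is not an actual-treatment rule either.

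**Conclusion.** The gap is real and minor. As written, a patient who takes the non-assigned insulin has safety and antibody outcomes counted against the wrong product, because neither document gives an as-received rule for safety. The likely effect is very small: 91.5% to 99.2% of a true difference is kept for 10 down to 1 switched patients per arm, and it is zero if no wrong product is taken. These figures assume the planned arm sizes of 353 and 177, switching for the whole treatment period, equal counts in both arms, and risk that follows the product taken. On the PP set, the documents support only that the protocol and SAP definitions differ and that the handling of mixed exposure is not stated in either.

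**What to change.** - Keep efficacy on the FAS as randomized.
- In SAP 5.2.1, define a safety set (randomized patients with at least one dose) grouped by study insulin actually received, and name it for the adverse event, hypoglycemia and immunogenicity analyses. It holds the same patients as the FAS; only the grouping differs.
- Fix a rule before database lock for patients who took both products, for example the product taken on most days, and list these patients. The trial is open-label, so the rule should not be chosen once the cases are known.
- For PP, align Protocol 12.2.1 with SAP 5.2.1 and state how wrong-product and mixed-exposure patients are handled, citing the TIMP if it already covers them.

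The cost is mainly wording. The SAP already needs an actual-treatment variable for PP; it would be derived for all treated patients. Protocol 12.2.1 lets changes to analysis methods that are not a principal feature be recorded and justified in the SAP, so whether a protocol amendment is needed is for the sponsor to judge. The downside is that the safety grouping is not strictly as randomized for the few patients affected.
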